## INNOVATION:

There are currently no data addressing the use or effectiveness of the LNG-IUS as a method of emergency contraception. This proposal will provide essential information to both patients and clinicians in this field. Specifically, the LIFE study (levonorgestrel IUS For Emergency contraception) will answer the following questions:

- 1) Is the LNG-IUS an effective method of emergency contraception?
- 2) Is the LNG-IUS more effective than the oral levonorgestrel regimen?
- 3) Are women receiving LNG-IUS more likely to be using a LARC method at 6 months?
- 4) Are women receiving the LNG-IUS as emergency contraception still using and satisfied with their method at 6 months and at 12 months?

Current practices in the United States provide women 4 choices of EC. A modified regimen of combined oral contraceptives (Yuzpe method) has been shown to be the least effective and associated with the most side-effects. There are two additional oral regimens, the levonorgestrel and ulipristal acetate regimens which are effective for a single act of unprotected intercourse. The most commonly-used method is the oral levonorgestrel regimen which is largely available over the counter. Ulipristal acetate is the newest regimen, approved by the FDA in August 2010, requires a physician prescription, and is more expensive than the levonorgestrel option. The most effective, least used and most expensive method of EC is the Cu-T380. This method, unlike the previous methods, provides continued highly effective long-term contraception. The levonorgestrel-IUS is the only other intrauterine device available in the U.S. The LNG-IUS is currently used only for standard contraception, not emergency contraception. In this setting it has been shown to be highly effective, convenient, forgettable, cost-effective, and extremely well-liked by users. *This research is innovative, because we will be evaluating a new method of emergency contraception and expanding access to include a well-liked, long-term, and extremely effective method of contraception that has the potential to reduce unintended pregnancy and abortion rates.* The American College of Obstetricians and Gynecologists Committee on Gynecologic Practice Opinion, published in 2009 suggested that the high rates of unintended pregnancy may be a direct consequence of low use of long acting reversible contraceptives.

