### **Research Design and Methodology:**

Research design and general methodological approach: We will perform a randomized control trial comparing oral UPA to LNG-IUS for emergency contraception. We will prospectively enroll 532 women experiencing an act of under-protected intercourse within the previous 5 days (120 hours). Participants with a negative pregnancy test, and who meet all inclusion criteria, will be randomized to either an immediate LNG-IUS insertion or oral UPA EC regimen (30mg ulipristal acetate) in a 3:1 ratio. Participants will be provided with a pregnancy test to perform at home and will be called to report the results of the urine pregnancy test 5-6 weeks after insertion. Participants receiving the LNG-IUS will also be return for a brief visit to check LNG-IUS strings. Participants will be contacted via telephone at 6 and 12months post enrollment to complete a follow-up survey. The primary outcome of this study is observed pregnancy rates at 5 weeks and 6 months after enrollment.

Criteria for selection of subjects: Potential participants for this study will be identified in as follows: 1) Women enrolled in the Contraceptive CHOICE Project (CHOICE) who are not currently using a long acting reversible contraceptive (LARC) method and have experienced an act of under-protected intercourse in the previous 5

days; 2) Women presenting, either in person or via telephone contact, to the Barnes Jewish Hospital Women's Health resident OB/GYN clinic who have experienced an act of under-protected intercourse in the previous 5 days; 3) Women identified from an advertising campaign; and

Enrollment: All potential participants receive informed consent and will be directed to make an appointment for consent, randomization, and allocation of method.

Inclusion Criteria:

- Women age 14-45
- Under-protected intercourse within the last five days (120 hours)
- Willingness to accept either IUS intervention or oral EC
- Ability and willingness to follow-up via telephone for results of a urine pregnancy test (UPT)
- Ability and willingness to be contacted by phone for 6 and 12 month follow-up

Exclusion Criteria:

- Positive pregnancy test
- Non-English speaking
- Contraindication to intrauterine contraception or oral UPA
  - Active cervicitis, PID, or recent post-abortal or postpartum infection
  - Undiagnosed abnormal uterine bleeding
  - Known or suspected cervical or endometrial neoplasia

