  - Known or suspected breast cancer or other progestin-sensitive cancer
  - Uterine anomalies that preclude IUD insertion
- Inability or unwillingness to comply with follow-up

Randomization: A permuted block randomization scheme will be created using the nQuery software (Statistical Solutions, Saugus, MA) using a computerized random number generator. Block sizes will vary, and will be balanced within each recruitment site. Assignment will be concealed in sealed, opaque envelopes. Participants will be randomly assigned to LNG-IUS or oral UPA with a 3:1 ratio.

Description of drugs and devices:

The U.S. Food and Drug Administration (FDA) approved the LNG-IUS in 2000 as a 5-year method of reversible contraception. The device contains 52 mg of levonorgestrel which is slowly released at a rate of 20 mcg/day into the uterus. The device is safe, effective and easy to use in almost all populations. The standard contraceptive mechanism of action is through cervical mucus thickening and endometrial lining suppression. The device has not yet been evaluated as a method of emergency contraception. However, the WashU study team submitted an IND application to the FDA, and obtained an IND to study the device as a method of EC. A clinician trained in IUD insertions will insert the LNG-IUS.

The FDA first approved oral levonorgestrel with a dedicated indication for emergency contraception in 1998. There are currently two acceptable dosing protocols, single-dose, and two-dose, both of which contain a total of 1.5 mg of levonorgestrel. There are several proposed mechanisms by which this regimen reduces pregnancy: inhibited or delayed ovulation, interference with sperm transport and penetration, and

endometrial changes decreasing receptivity. It has been shown to have no effect on an already established pregnancy and is not a form of medical abortion.

The FDA approved Ulipristal acetate in August 2011(ulipristal acetate) is a synthetic progesterone agonist/antagonist. When taken immediately before ovulation is to occur, Ella postpones follicular rupture. The likely primary mechanism of action of ulipristal acetate for emergency contraception is therefore inhibition or delay of ovulation; however, alterations to the endometrium that may affect implantation may also contribute to efficacy.

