### **Power Analysis and Sample Size**

Power analysis and Sample size calculation was performed with Epi-Info v 6.0.

**Sample Size:** With an alpha ( $\alpha$ ) = 0.05, power of 90%, and assuming unintended pregnancy rates (total 5 weeks through 6 months) of 11% for the oral UPA regimen and 2% for the LNG-IUS, and a 3:1 ratio of LNG-IUS allocation to UPA, we calculate our sample size to be 532 participants (399 LNG-IUS and 133 UPA). This accounts for approximately 20% loss to follow-up rate by 6 months. We chose a 3:1 ratio of LNG-IUS to UPA to allow for a more precise estimate of immediate failure rates of the LNG-IUS group.

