### **Data Analysis/Statistical Methods:**

**Preliminary Analysis:** Descriptive analyses will include comparison of the baseline characteristics of participants in the two treatment arms. Continuous variables will be summarized using means, medians, and standard deviations. Categorical variables will be presented as frequencies. Continuous variables that are normally distributed will be analyzed with Students t-test, and nonparametric tests will be used for those that are not normally distributed. Chi-square and Fisher's exact tests will be used to analyze categorical variables.

**Primary Aim:** Observed pregnancies at 5-6 weeks and at 6 months in the LNG-IUD group will be compared to those in the oral UPA group. The analysis population is enrolled women who complete 5-6-week and 6 month follow-up. "Modified" intent to treat analysis will be used. Pregnancies will be presented as frequencies and chi-square tests will be used for analysis. We expect the two groups to be balanced on important confounding variables such as menstrual cycle day at the time of unprotected intercourse. However, if there are significant imbalances, stratified or multivariable analysis will be performed. Pregnancies at 5-6 weeks and 6 months will be compared by intervention arm with Kaplan-Meier estimates, using dating from last menstrual period time. Logistic regression will be used to control for confounding (if necessary) using the dichotomous outcome of pregnancy (yes/no) at each time point.

**Secondary Aim1:** Descriptive analyses will be used to compare demographic characteristics of participants who screen eligible, but decline to participate and those who enroll in the study. Reasons for declining participation will also be collected and qualitatively evaluated for recurrent themes.

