### Pregnancy

UPA is 93-94% effective in preventing pregnancy

LNG-IUS: We hypothesize the LNG-IUS will be as effective as the Copper IUD for EC

If participant reports a positive pregnancy test, we will: 1) invite the participant in for pregnancy testing and transvaginal ultrasound to confirm location and dating of pregnancy. If the LNG-IUS is in place and intrauterine pregnancy is confirmed, we will recommend and complete removal of IUD.

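### The 5-6 week comparison counts all pregnancies and does not isolate failures for the index act, so a difference favouring the LNG-IUS could arise with equal efficacy as emergency contraception

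*Combined protocol and SAP*

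**What the plan says.** All references are to the combined protocol and SAP.

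- **Comparison.** For the primary aim, Data Analysis/Statistical Methods states: "Observed pregnancies at 5-6 weeks and at 6 months in the LNG-IUD group will be compared to those in the oral UPA group". What is counted is pregnancy after treatment, whatever act caused it.
- **Use of the early result.** The hypothesis under APPROACH has two parts: performance as EC, and pregnancy through 6 months. Power Analysis and Sample Size justifies the 3:1 allocation by the precision it gives for early failure of the LNG-IUS. Risks and Benefits also speaks of immediate failures and calls an urgent DSMB meeting once the LNG-IUS arm has more than one pregnancy.
- **Eligibility.** The inclusion criterion is "Under-protected intercourse within the last five days (120 hours"). No criterion addresses earlier acts in the same cycle.
- **Cover after treatment.** INNOVATION: "There are two additional oral regimens, the levonorgestrel and ulipristal acetate regimens which are effective for a single act of unprotected intercourse". The drug description gives UPA's likely "primary mechanism of action of ulipristal acetate for emergency contraception is therefore inhibition or delay of ovulation". The Enrollment clinic visit offers UPA women a prescription for ongoing pills but does not require it.
- **Dating.** A woman who reports a positive test is invited for testing and "transvaginal ultrasound to confirm location and dating of pregnancy" (Risks and Benefits, Pregnancy). Dating from the last menstrual period (LMP) is named for the Kaplan-Meier estimates. Neither is used to decide which pregnancies are failures for the index act.

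**The concern.** The 5-6 week count is the only planned measure of the EC part of the hypothesis. It pools three kinds of pregnancy: conceived before the 120-hour window, from the index act, and from acts after treatment.

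The third kind differs by arm. The LNG-IUS keeps protecting. A woman given UPA whose ovulation is delayed and who does not take up the pills is exposed again in the same cycle. That is an effect of continuing contraception, which the 6-month comparison rightly credits to the LNG-IUS, but it says nothing about efficacy for the index act.

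The first kind arises equally in both arms in expectation. It creates no difference on its own, but it raises both absolute rates, including the LNG-IUS early failure rate that the allocation ratio was chosen to estimate.

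With few early pregnancies expected, reassigning one or two could change what the trial says about the LNG-IUS as EC.

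**Working it through.** **1. The plan's own figure.** Inputs from Power Analysis and Sample Size: alpha and power "0.05, power of 90"%; "11% for the oral UPA regimen and 2% for the LNG-IUS"; ratio 3:1; about 20% loss. Sidedness is not stated; two-sided is assumed. With r = 3, difference 0.09 and pooled rate (0.11 + 3 × 0.02)/4 = 0.0425:

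- n(UPA) = [1.96 √(4 × 0.0425 × 0.9575) + 1.2816 √(3 × 0.11 × 0.89 + 0.02 × 0.98)]² / (3 × 0.09²) ≈ 94.
- The continuity correction raises this to 108, so the total is 108 + 324 = 432.
- 432/0.8 = 540, against 532 stated, a difference of 8 (1.5%).

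The figure reproduces closely. Its rates are "unintended pregnancy rates (total 5 weeks through 6 months"), so attribution of early pregnancies does not enter it.

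**2. Acts after treatment.** From the plan: 11% for UPA through 6 months. Assumed, because the documents give no 5-week rate:

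- index-act failure f is the same in both arms, 1% or 2%;
- the rest of the 11% accrues evenly over T = 24 to 26 weeks;
- conception to positive test takes 2 weeks, so acts in the first 3 of 5 weeks count;
- the LNG-IUS has no conceptions from later acts.

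Added points = (11 − f) × 3/T. Apparent ratio = (f + added)/f.

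| f | T | Added | UPA vs LNG-IUS | Ratio |
|---|---|---|---|---|
| 1% | 26 | 10 × 3/26 = 1.15 | 2.15% vs 1% | 2.2 |
| 1% | 24 | 10 × 3/24 = 1.25 | 2.25% vs 1% | 2.3 |
| 2% | 26 | 9 × 3/26 = 1.04 | 3.04% vs 2% | 1.5 |
| 2% | 24 | 9 × 3/24 = 1.13 | 3.13% vs 2% | 1.6 |

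With 133 × 0.8 ≈ 106 UPA women followed, this is 1.1 to 1.3 women.

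Two sensitivities:

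- *LNG-IUS later conceptions.* At f = 1% the plan's 2% total leaves the LNG-IUS 1 point for later acts. Spread the same way, this adds 3/26 to 3/24 = 0.12 to 0.13 points, and the ratio falls to about 1.9-2.0. At f = 2% nothing is left and the ratio is unchanged.
- *No detection lag.* Five weeks of exposure over T = 26 add 10 × 5/26 = 1.92 or 9 × 5/26 = 1.73 points, giving ratios of 2.9 or 1.9.

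**3. Acts before the window.** Let b be the pre-window conception rate, equal by randomisation. Observed risk = 1 − (1 − f)(1 − b).

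- *Equal f.* f = 1% and b = 0.5% give 1.5% in both arms, ratio 1. No difference is created.
- *Unequal f (assumed 1.5% vs 0.1%, ratio 15).* b = 0.5% gives 1.99% vs 0.60%, ratio 3.3. b = 1% gives 2.49% vs 1.10%, ratio 2.3.
- *LNG-IUS alone.* Among 399 women, b = 0.25% adds 1.0 pregnancy and b = 0.5% adds 2.0. The chance of two or more, 1 − (1 − b)³⁹⁹ − 399b(1 − b)³⁹⁸, is 26% or 59% with no index-act failure at all. Two pregnancies are enough to call the urgent DSMB meeting.

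**The case against.** The strongest reply is that the stated aim is effectiveness judged by observed pregnancy rates, and the hypothesis runs through 6 months. Continued protection is part of what the LNG-IUS offers, so counting every pregnancy by arm answers that aim. This stands. Apart from the restriction to women who complete follow-up, which is a separate matter, the comparison validly estimates the effect of assignment. It does not isolate index-act failure, and the early result is also read that way.

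Four stronger readings might be inferred, and the documents do not support them:

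- *Every positive test is recorded as an EC failure.* Home positives are to be validated at the site (Evaluation/Follow-Up, Measures), and no passage states such a classification.
- *Earlier conceptions bias the comparison between arms.* They are balanced at randomisation. A caveat is that BACKGROUND & SIGNIFICANCE proposes post-fertilisation effects for the LNG-IUS, so the number surviving to a positive test might differ.
- *Earlier acts go unrecorded.* The enrolment questionnaire and clinical forms are not in the documents and may record them. The analysis section implies that cycle day at intercourse is known.
- *The size of the distortion can be calculated.* It cannot. Take-up of the offered pills would lower the risk from later acts, delayed ovulation could bring it forward, and the steady accrual is an assumption.

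The objection also limits the remedy. Dating is by invitation, recalled acts come from women who know their arm, and dating may not separate the index act from one a few days later. An index-compatible count therefore should not replace the randomised one.

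**Conclusion.** The point holds as a gap in attribution. The plan reads early pregnancies as evidence on EC failure but has no rule to identify failures for the index act. Later acts can produce a 5-week difference favouring the LNG-IUS with equal index-act efficacy: about 1.0-1.3 points and an apparent ratio of about 1.5-2.3. That range rests on assumed index-act failure of 1-2%, even accrual, a 2-week detection lag and no later conceptions with the LNG-IUS. It shows an order of magnitude and is not an estimate.

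Earlier acts work differently: they dilute the ratio and inflate the absolute LNG-IUS failure rate without creating a difference. The all-pregnancy comparisons at 5-6 weeks and 6 months remain valid as effects of assignment. What the plan cannot yet support is a statement about efficacy for the index act.

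**What to change.** 1. Keep the all-pregnancy comparison by arm as randomised at 5-6 weeks and 6 months.
2. In Data Analysis/Statistical Methods, Primary Aim, add a rule fixed before early results are seen and applied without knowledge of arm. It classifies each confirmed pregnancy from ultrasound and LMP dating as conceived before the index window, compatible with the index act, later, or undeterminable.
3. Report the index-compatible 5-week count by arm beside the all-pregnancy count, with undeterminable cases counted both ways. Base any statement about EC efficacy for the index act on both counts.
4. Record the dates of under-protected acts since the last menstrual period at enrolment, if the forms do not already do so, and acts since enrolment at the 5-week call.

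The cost is at most two survey items and one paragraph of analysis text; the ultrasound is already planned. The downside is very few events, some pregnancies that are undated or cannot be separated from nearby acts, and reliance on dates recalled by unblinded women. The sample size does not change.

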#### Evaluation/ Follow-Up:

At enrollment all women will undergo a highly sensitive urine pregnancy test as well as self-collected vaginal swab for sexually transmitted disease (STI) testing for *Neisseria gonorrhoeae* and *Chlamydia trachomatis*. Randomization and allocation of emergency contraceptive method will occur immediately following consent. A positive test for an STI will not exclude the patient from participation. All positive *N. gonorrhoeae* or *C. trachomatis* tests will be treated with standard CDC-approved treatment. Partner treatment will also be offered. Women randomly assigned to the LNG-IUS group will be asked to return at 5-6 weeks for a string check. All participants will be provided a urine pregnancy test at enrollment and will be called at 5 weeks post enrollment to obtain results. Participants will then be contacted to complete a follow-up surveys at 6 and 12 months following enrollment.

Measures: Urine pregnancy test results will be documented at 5-6 weeks following method allocation. Negative urine pregnancy tests will be validated by a normal menses after enrollment. Participants testing positive at home will be asked to come into the study site for pregnancy test validation and options counseling. We have studied over 9,000 women attempting to avoid unintended pregnancy in the Contraceptive CHOICE Project. Participants were able and willing to report home pregnancy testing results and/or return for a visit for a sensitive pregnancy test. Any woman who suspects pregnancy, is late for her routine menstrual cycle, or who reports a positive home test will be asked to return to our clinic for pregnancy test validation and options counseling (offered option of continuing the pregnancy or pregnancy termination). *We are using the CONSULT urine pregnancy test which is sensitive to a hcg level of 20mIU/mL with a specificity of >99% (Appendix A).*

Women enrolled in an EC study are clearly motivated to avoid an unintended pregnancy. A negative home pregnancy test and regular menses reliably excludes an on-going pregnancy. Self-report of a negative test and menses will not be validated, as they are acceptable measures to reliably exclude pregnancy. Pregnancy

testing in this protocol has been used for the CHOICE project, with two peer-reviewed publications accepted to the New England Journal of Medicine (Winner B. et al. 2012 & Secura G. et al. 2014)

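### The primary analysis set is limited to women who complete follow-up, so a pregnancy already confirmed at 5 weeks can drop out of the cumulative 6-month comparison

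*Combined protocol and SAP*

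**What the plan says.** The Primary Aim paragraph under Data Analysis/Statistical Methods gives one population: "The analysis population is enrolled women who complete 5-6-week and 6 month follow-up". The next sentence calls the analysis modified intention to treat and does not define the modification. Three methods follow:

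- A crude comparison of proportions: "Pregnancies will be presented as frequencies and chi-square tests will be used for analysis".
- A time-to-event comparison: "Pregnancies at 5-6 weeks and 6 months will be compared by intervention arm with Kaplan-Meier estimates, using dating from last menstrual period time".
- A logistic model of pregnancy status, fitted separately at the two assessments and held in reserve in case the arms turn out to be confounded.

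The earlier section, Statistical Approach & Data Analysis, names only logistic regression for the primary aim and gives no population.

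The primary outcome is unintended pregnancy at both 5 weeks and 6 months. The sample size uses rates that accumulate through 6 months, 11% for UPA and 2% for LNG-IUS. On loss, it adds: "This accounts for approximately 20% loss to follow-up rate by 6 months". Pregnancies found at 5 weeks are confirmed in person: "Participants testing positive at home will be asked to come into the study site for pregnancy test validation and options counseling".

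On missing women, the plan compares those lost with the baseline sample on demographics and method type and will consider the effect on interpretation. The Retention Plan tries to limit loss. The only censoring rule sits under LARC use.

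**The concern.** Whether a woman counts depends on her answering calls made after randomisation. For a cumulative outcome, a pregnancy validated at 5 weeks settles her 6-month status, and a missed call later does not make it unknown. The rule can therefore discard observed primary events, and it leaves the randomised comparison exposed to any link between pregnancy, arm and response.

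Two further gaps come from the same wording. First, a set of completers leaves the Kaplan-Meier analysis with little or nothing to censor. It is also unclear whether the last menstrual period dates the pregnancy or sets time zero. Second, under Enrollment the pelvic examination that decides whether the LNG-IUS is inserted comes after randomisation, and the plan does not say whether women not inserted stay in their assigned arm.

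Few events are expected, so single ones matter, particularly for the estimate that drove the allocation: "We chose a 3:1 ratio of LNG-IUS to UPA to allow for a more precise estimate of immediate failure rates of the LNG-IUS group".

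**Working it through.** **Inputs from the plan.** 11% (UPA) and 2% (LNG-IUS) through 6 months; 133 and 399 women; 3:1 allocation; alpha 0.05; 90% power; about 20% loss by 6 months. Sidedness is not stated; two-sided is assumed.

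**The plan's own figure.** The weighted mean rate is (0.11 + 3 × 0.02)/4 = 0.0425.

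- Before correction, UPA n = {1.96√[0.0425 × 0.9575 × 4/3] + 1.2816√[0.11 × 0.89 + 0.02 × 0.98/3]}² / 0.09² = (0.4566 + 0.4142)² / 0.0081 ≈ 93.6.
- The continuity correction gives (93.6/4){1 + √[1 + 8/(93.6 × 3 × 0.09)]}² ≈ 108.
- The total is 108 + 324 = 432. Dividing by 0.80 gives 540; multiplying by 1.20 gives 520. The stated 532 is within 3% of both, so it is reproduced and is not in question.

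**Assumptions for the illustration.** The plan gives no 5-week rates and no loss by pregnancy status. I assume that all women respond at week 5, half of the pregnancies are known by then, and 20% of all other women are lost later. L is the share of women with a known 5-week pregnancy who miss the 6-month call.

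**Events kept.**

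| | UPA | LNG-IUS |
|---|---|---|
| True events | 133 × 0.11 = 14.6 | 399 × 0.02 = 8.0 |
| Completers only, L = 20% | 14.63 × 0.80 = 11.7 | 7.98 × 0.80 = 6.4 |
| Known pregnancies kept | 14.63 × (0.5 + 0.5 × 0.8) = 13.2 | 7.98 × 0.9 = 7.2 |

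**6-month completer rate.** With k = 0.5(1 − L) + 0.5 × 0.8, the rate is pk / [pk + 0.8(1 − p)]. For UPA at L = 40%: 0.11 × 0.7 / (0.077 + 0.712) = 9.76%.

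| L (UPA / LNG-IUS) | UPA | LNG-IUS | Risk ratio |
|---|---|---|---|
| 20% / 20% | 11.0% | 2.0% | 0.182 |
| 10% / 10% | 11.6% | 2.1% | 0.183 |
| 40% / 40% | 9.8% | 1.75% | 0.180 |
| 40% / 20% | 9.8% | 2.0% | 0.205 |
| 20% / 40% | 11.0% | 1.75% | 0.159 |

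Simulated power of the uncorrected chi-square test on completers (20,000 runs per case) is about 95% with 20% in both arms, about 90% with 40% in UPA only, and about 96% to 97% with 40% in LNG-IUS only. Kaplan-Meier with known events kept averages 11.0% and 2.0% in all five patterns, with log-rank power of about 97%. That agreement follows from the assumed loss pattern: full week-5 response, and later loss unrelated to pregnancy.

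**A more extreme case.** Assume 5-week rates of 6% and 1%, with 80% of known UPA pregnancies and 20% of known LNG-IUS pregnancies missing the later call. UPA becomes (0.06 × 0.2 + 0.05 × 0.8) / (0.052 + 0.712) = 6.8% against 2.0%, a risk ratio of 0.29. Reversing the two shares gives 11.0% against 1.3%, a risk ratio of 0.11.

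**5 weeks, if both contacts are required.** Assume two known LNG-IUS failures, one of whom misses the 6-month call. The rule gives 1/319 = 0.31% (exact 95% CI 0.01% to 1.73%). Using every known status at 90% to 100% response gives 2/359 = 0.56% (0.07% to 2.00%) to 2/399 = 0.50% (0.06% to 1.80%). The intervals overlap widely.

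**The case against.** The strongest defence is that a woman with a validated pregnancy has reached the endpoint and so has completed follow-up for it. A cumulative outcome and a planned Kaplan-Meier analysis are consistent with that reading. The text does not exclude it, but it does not state it either, and the words used are about completing contacts. The completer sentence may also be meant as the definition of the modification. Even so, it leaves open whether women are analysed as randomised.

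The second defence is size, and it stands. With equal loss in both arms the risk ratio stays between 0.180 and 0.183 against a true 0.182, and 40% loss in UPA alone still leaves about the 90% power the design asked for. Larger distortion needs strong, arm-specific loss among women known to be pregnant, for which the plan gives no figure.

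Third, the chi-square test is not invalid in itself. Keeping known pregnancies while dropping non-pregnant women lost later would raise the rates to 12.2% and 2.24%, but the ratio would be 0.184. The case for Kaplan-Meier rests on the absolute rates, not on the chi-square comparison failing.

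Finally, the rule that more than one LNG-IUS pregnancy triggers an urgent DSMB meeting brings such events to light, but it does not say how they are counted.

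**Conclusion.** The point holds as a defect in the analysis-set rule and should be fixed. Followed as written, the rule conditions the primary comparison on response after randomisation and can discard confirmed events. No other section corrects this.

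A reader might infer that the 6-month result will be biased, or biased in favour of one arm. The documents do not support that: if loss is unrelated to pregnancy only events and precision are lost, and otherwise the direction depends on which arm loses more known pregnancies. A reader might also infer that such a pregnancy is lost on every possible reading, or that the modification excludes women who were not inserted. The plan is silent on both.

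Confidence is high about the wording and low about the size. Every rate and power figure beyond the plan's own inputs rests on assumed week-5 response, timing of pregnancies and loss pattern. On those assumptions the effect is modest unless loss is strongly related to pregnancy.

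**What to change.** - **Set.** Define the primary set as all randomised women with a negative enrolment test, analysed in the assigned arm whether or not the LNG-IUS was inserted.
- **5-6 weeks.** Use every woman whose status is known.
- **6 months.** Use the planned Kaplan-Meier analysis with time from randomisation. Count every known pregnancy as an event and censor other women at last contact. Use 12-month answers only where they establish 6-month status, for pregnant and non-pregnant women alike; the plan does not show how precisely those pregnancies are dated.
- **Dating.** State that the last menstrual period only dates the pregnancy. Say how a pregnancy dated to on or before randomisation is entered, since intercourse may precede enrolment by up to 120 hours.
- **Consistency.** Base the 6-month arm comparison on this analysis, align the logistic regression in Statistical Approach & Data Analysis with it, and keep the completer chi-square as a sensitivity analysis.

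The cost is rewording and some programming; the sample size and visits do not change. There are downsides. Women not inserted slightly dilute the LNG-IUS estimate. Censoring still assumes that loss is unrelated to pregnancy, so unreported pregnancies would bias rates downward. Pregnant women who report between calls, while non-pregnant women are censored, would bias them upward. On the working's assumptions, if 25%, 50% or 100% of otherwise-lost later UPA pregnancies were reported this way, 11% would become 11.3%, 11.6% or 12.3%. Detection may also differ by arm: "Women randomly assigned to the LNG-IUS group will be asked to return at 5-6 weeks for a string check".
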